4. SUBJECT DISPOSITION

4.1. Subject Enrollment and Disposition

A summary of subject enrollment will be provided for each country and investigator within a country, by treatment group and overall. The summary will present the number and percentage of subjects enrolled. For each column, the denominator for the percentage calculation will be the total number of subjects analyzed for that column.

A similar enrollment table will be provided by randomization stratum. The denominator for the percentage of subjects in the stratum will be the total number of randomized subjects. If there are discrepancies in the value used for stratification assignment between the IXRS and the clinical database, the value collected in the clinical database will be used for the summary. A listing of subjects with discrepancies in the value used for stratification assignment between the IXRS and the clinical database at the time of data finalization will be provided.

The randomization schedule used for the study will be provided as an appendix to the CSR.

A summary of subject disposition will be provided by treatment group and study phase. This summary will present the number of subjects screened, the number of subjects randomized, and the number of subjects in each of the categories listed below:

- Safety Analysis Set;
- Completed study drug in the BD Phase;
- Did not complete study drug with reasons for premature discontinuation of study drug in BD Phase,
- OLE Analysis Set
- Continuing study drug in the OLE Phase (remove for final analysis);
- Completed study drug in the OLE Phase;
- Did not complete study drug with reasons for premature discontinuation of study drug in the OLE Phase.
- Continuing study (remove for final analysis);
- Completed study;
- Did not complete the study with reasons for premature discontinuation of study.

For the status of study drug and study completion and reasons for premature discontinuation, the number and percentage of subjects in each category will be provided. The denominator for the percentage calculation will be the total number of subjects in the Safety Analysis Set/OLE Analysis Set corresponding to that column in that study phase. In addition, a flowchart will be provided to depict the disposition.

The following by-subject listings will be provided by subject ID number in ascending order to support the above summary tables:

- Reasons for premature study drug discontinuation in each study phase or study discontinuation
- Reasons for screen failure will be provided by screening ID number in ascending order
- Lot number and kit ID

4.2. Extent of Study Drug Exposure and Adherence

Extent of exposure to study drug will be examined by assessing the total duration of exposure to study drug and the level of adherence to the study drug specified in the protocol.

4.2.1. Duration of Exposure to Study Drug

For each study phase, total duration of exposure to study drug will be defined as last dose date minus first dose date plus 1 of the reporting phase, regardless of any temporary interruptions in study drug administration, and will be expressed in weeks using up to 1 decimal place (eg, 4.5 weeks). When summarizing cumulative exposure in LT analysis, the sum of exposure in the BD Phase and OLE Phase is used. If the last study drug dose date is missing, the latest date among the study drug end date, clinical visit date, laboratory sample collection date, and vital signs assessment date that occurred during the on-treatment period will be used.

The total duration of exposure to study drug will be summarized using descriptive statistics and using the number (ie, cumulative counts) and percentage of subjects exposed through the following time periods: 1 day, 4 weeks, 8 weeks, and 12 weeks in the BD Phase; 1 day, 4 weeks, 12 weeks, 24 weeks, and every 12 weeks thereafter in the OLE Phase. Summaries will be provided by treatment groups 1 – 4 for the Safety Analysis Set in the BD Phase, 5 – 8 for the OLE Analysis Set in the OLE Phase, and 9 – 10 for the LT analysis, as defined in Section 3.1 and Section 3.2.

No formal statistical testing is planned.

4.2.2. Adherence to Study Drug

The total number of doses administered will be summarized using descriptive statistics.

The presumed total number of doses administered to a subject will be determined by the data collected on the drug accountability CRF using the following formula:

$$\begin{aligned} \text{Total Number of Doses Administered} = \\ \left(\sum \text{No. of Doses Dispensed} \right) - \left(\sum \text{No. of Doses Returned} \right) \end{aligned}$$

4.2.2.1. Adherence in the BD Phase

Prescribed adherence rate will be calculated for the BD Phase and will be provided by treatment groups 1, 2, and 4 by type of tablet for the Safety Analysis Set in the BD Phase. The level of prescribed adherence to the study drug regimen will be determined by the total amount of study drug administered relative to the total amount of study drug specified by the protocol for a subject who completes treatment in the BD Phase.

The level of prescribed adherence will be expressed as a percentage using the following formula:

$$\text{Prescribed Adherence (\%)} = \left(\frac{\text{Total Amount of Study Drug Administered}}{\text{Total Amount of Study Drug Specified by Protocol}} \right) \times 100$$

Total amount of study drug specified by protocol for the BD Phase is 84 for each type of tablet. Descriptive statistics for the level of prescribed adherence with the number and percentage of subjects belonging to adherence categories (< 75%, ≥ 75 to < 90%, ≥ 90%) will be provided.

4.2.2.2. Adherence in the OLE Phase

On-treatment adherence rate will be calculated for the OLE Phase and will be provided by treatment groups 5 – 8 for the OLE Analysis Set in the OLE Phase. The level of on-treatment adherence to the study drug regimen will be determined by the total amount of study drug administered relative to the total amount of study drug expected to be administered during a subject's actual on-treatment period.

The level of on-treatment adherence will be expressed as a percentage using the following formula:

$$\text{On-Treatment Adherence (\%)} = \left(\frac{\text{Total Amount of Study Drug Administered}}{\text{Study Drug Expected to be Administered on Treatment}} \right) \times 100$$

On-Treatment adherence will be calculated based on overall tablets administered, regardless of the type of the tablets in OLE Phase. Descriptive statistics for the level of on-treatment adherence with the number and percentage of subjects belonging to adherence categories (< 75%, ≥ 75 to < 90%, ≥ 90%) will be provided.

No formal statistical testing is planned.

A by-subject listing of study drug administration and drug accountability will be provided separately by subject ID number (in ascending order) and visit (in chronological order).

4.3. Protocol Deviations

Subjects who did not meet the eligibility criteria for study entry, but enrolled in the study will be summarized regardless of whether they were exempted by the sponsor or not. The summary will present the number and percentage of subjects who did not meet at least 1 eligibility criterion and the number and percentage of subjects who did not meet specific criteria by treatment group based on the All Randomized Analysis Set. A by-subject listing will be provided for those subjects who did not meet at least 1 eligibility (inclusion or exclusion) criterion. The listing will present the eligibility criterion (or criteria if more than 1 deviation) that subjects did not meet and related comments, if collected.

Protocol deviations occurring after subjects entered the study are documented during routine monitoring. The number and percentage of subjects with important protocol deviations by deviation reason (eg, nonadherence to study drug, violation of select inclusion/exclusion criteria) will be summarized by treatment group for the All Randomized Analysis Set/OLE Analysis Set per study phase. A by-subject listing will be provided for those subjects with any important protocol deviation.

5. BASELINE CHARACTERISTICS

5.1. Demographics

Subject demographic variables (ie, age, sex, race, and ethnicity) will be summarized by treatment group and overall using descriptive statistics for age, and using number and percentage of subjects for sex, race, and ethnicity. The summary of demographic data will be provided for the Safety Analysis Set for the BD phase.

A by-subject demographic listing, including the informed consent date, will be provided by subject ID number in ascending order.

5.2. Baseline Characteristics

Other baseline characteristics include:

- Body weight
- Height
- Body mass index (BMI) as a continuous variable and by categories ($< 18.5 \text{ kg/m}^2$, $18.5 \text{ to } < 25 \text{ kg/m}^2$, $25 \text{ to } < 30 \text{ kg/m}^2$ and $\geq 30 \text{ kg/m}^2$)
- UDCA use (Yes or No, based on concomitant medication page)
- ALP as a continuous variable
- Total bilirubin as a continuous variable and by categories ($\leq \text{ULN}$ or $> \text{ULN}$)
- Direct bilirubin
- ALT as a continuous variable and by categories ($< \text{ULN}$ and $\geq \text{ULN}$)
- AST as a continuous variable and by categories ($< \text{ULN}$ and $\geq \text{ULN}$)
- GGT
- Fasting serum glucose
- Fasting insulin
- Homeostatic assessment of insulin resistance (HOMA-IR)
- Hemoglobin A1c (HbA1c)
- Fasting triglycerides

- Total cholesterol
- High density lipoprotein-cholesterol (HDL-C)
- Calculated fasting low density lipoprotein-cholesterol (LDL-C)
- Calculated fasting very low density lipoprotein-cholesterol (VLDL-C)
- Calculated fasting non high density lipoprotein-cholesterol (Non-HDL-C)
- ELF™ score and components (hyaluronic acid [HA], procollagen III amino terminal peptide [PIIINP], tissue inhibitor of metalloproteinase 1 [TIMP-1])
- FibroSURE/FibroTest® and selected components (α_2 -macroglobulin, haptoglobin, apolipoprotein A1)
- FibroScan®
- hsCRP
- Fasting total bile acids
- Albumin
- INR
- Platelets
- Creatinine
- Smoking status at baseline
- Diabetes mellitus diagnosis at baseline (yes or no, based on medical history page)
- Taking hypertension treatment at baseline (yes or no, based on prior and concomitant medication page)
- Inflammatory bowel disease (IBD) history (yes or no, based on medical history page)
- Baseline partial Mayo score for patients with IBD history
- Baseline classification of biliary tree disease due to PSC based on MRCP

These baseline characteristics will be summarized by treatment groups 1 – 4 and overall (Section 3.2) using descriptive statistics for continuous variables and using number and percentage of subjects for categorical variables. The summary of baseline characteristics will be provided for the Safety Analysis Set. In addition, baseline characteristics will be summarized by baseline UDCA use in a separate table. No formal statistical testing is planned.

The tables will be repeated for the OLE Phase by treatment groups 5 – 8 in Section 3.2, except for height, fasting insulin, HOMA-IR, HbA1c, FibroScan, smoking status, diabetes diagnosis, IBD history and baseline classification of biliary tree disease due to PSC based on MRCP, which are not collected in the OLE Phase.

A by-subject listing of baseline characteristics will be provided by subject ID number in ascending order.

[figure not shown]
5.3. Medical History

General medical history data will be collected at screening and listed only. General medical history data will not be coded.

[figure not shown]
6. EFFICACY ANALYSES

Efficacy data will be summarized and analyzed based on the FAS for the BD Phase using treatment groups 1, 2, 4. Data from the OLE Phase will be summarized based on the OLE Analysis Set using treatment groups 5 – 8. For the LT analysis, data will be summarized using treatment groups 9 – 10. Refer to Section 3.2 for the detailed grouping of subjects.

[figure not shown]
6.1. Exploratory Efficacy Endpoints in the BD Phase

PPD

PPD

PPD

PPD

PPD
PPD

PPD

PPD

6.2. Exploratory Efficacy Endpoints in OLE Phase

PPD

[figure not shown]
13

PPD

PPD

PPD

[figure not shown]

6.3. Exploratory Efficacy Endpoints in Long Term Analysis

[figure not shown]
PPD

PPD

PPD

[figure not shown]
PPD

PPD

[figure not shown]
PPD || || 

PPD || 

6.4. Subgroup Analysis of the Exploratory Efficacy Endpoints

PPD || 

 || 

 || 

 || 

PPD || 

 || 

 || 

[figure not shown]
 || 

 || 

 || 

6.5. Change From Protocol-Specified Efficacy Analyses

PPD

7. SAFETY ANALYSES

Safety data will be summarized based on the Safety Analysis Set for the BD Phase using treatment groups 1 – 4 in Section 3.2, and the LT analysis using treatment groups 9 – 10. Data from OLE Phase will be summarized based on the OLE Analysis Set using treatment groups 5 – 8. Refer to Section 3.2 for the detailed grouping of subjects.

7.1. Adverse Events and Deaths

7.1.1. Adverse Event Dictionary

Clinical and laboratory adverse events (AEs) will be coded using the current version of MedDRA. System organ class (SOC), high-level group term (HLGT), high-level term (HLT), preferred term (PT), and lower-level term (LLT) will be provided in the AE dataset.

7.1.2. Adverse Event Severity

Adverse events are graded by the investigator as Grade 1, 2, 3, 4, or 5 according to toxicity criteria specified in the protocol. The severity grade of events for which the investigator did not record severity will be categorized as “missing” for tabular summaries and data listings. The missing category will be listed last in summary presentation.

7.1.3. Relationship of Adverse Events to Study Drug

Related AEs are those for which the investigator selected “Related” on the AE CRF to the question of “Related to Study Treatment.” Relatedness will always default to the investigator’s choice, not that of the medical monitor. Events for which the investigator did not record relationship to study drug will be considered related to study drug for summary purposes. However, by-subject data listings will show the relationship as missing.

7.1.4. Serious Adverse Events

Serious adverse events (SAEs) will be identified and captured as SAEs if the AEs met the definitions of SAEs that were specified in the study protocol. SAEs captured and stored in the clinical database will be reconciled with the SAE database from the Gilead Drug Safety and Public Health Department before data finalization.

7.1.5. Treatment-Emergent Adverse Events

7.1.5.1. Definition of Treatment-Emergent Adverse Events

Treatment-emergent adverse events (TEAEs) are defined as 1 or both of the following:

- Any AEs with an onset date on or after the study drug start date and no later than 30 days after permanent discontinuation of study drug in the BD Phase (and before the first dosing date in the OLE Phase)/OLE Phase.
- Any AEs leading to premature discontinuation of study drug in the BD/OLE phase.

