1.2. Study Design

This is a Phase 2 randomized, double-blind, placebo-controlled study evaluating the safety, tolerability, and efficacy of GS-9674 in subjects with PSC without cirrhosis.

[figure not shown]
The study consists of 2 phases, a BD Phase and an OLE Phase.

BD Phase: Includes a 4-week screening period, 12 weeks of blinded treatment, and a BD Phase follow-up visit 4 weeks after completion of blinded treatment.

Subjects completing the Blinded Study Phase without permanently discontinuing study drug will be eligible to participate in the OLE Phase of the study. OLE Phase: Includes a 96-week OLE treatment and an OLE Phase follow-up visit 4 weeks after completion of open label treatment.

The overall study design is presented graphically in [Figure 1-1](#).

Figure 1-1. Overall Study Design

Eligible subjects are randomly assigned to 1 of the following 3 treatment groups in a 2:2:1 ratio:

- GS-9674 30 mg + PTM GS-9674 100 mg orally once daily (n = 20);
- GS-9674 100 mg + PTM GS-9674 30 mg orally once daily (n = 20);
- PTM GS-9674 30 mg + PTM GS-9674 100 mg orally once daily (n = 10).

where PTM stands for Placebo to Match.

Central randomization is used. The randomization schedule is stratified by the presence or absence of ursodeoxycholic acid (UDCA) use.

Study drugs are administered for a total of 12 weeks from the Baseline/Day 1 visit during the BD Phase and 96 weeks during the OLE Phase. During the OLE Phase, subjects begin with open label treatment of GS-9674 (100 mg once daily). The dose of GS-9674 may be reduced from 100 mg to 30 mg (or subsequently increased back to 100 mg) at the principal investigator's (PI) discretion with the approval of the medical monitor, as required.

Subjects will be unblinded to their BD Phase treatment assignment after the primary analysis has been completed, approximately 6 weeks after all subjects have completed the BD Phase or early terminated. The schedule of assessments is provided as an appendix to this analysis plan ([Appendix 1](#)).

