7.1.5.2. Incomplete Dates

If the onset date of the AE is incomplete and the AE stop date is not prior to the first dosing date of study drug, then the month and year (or year alone if month is not recorded) of onset determine whether an AE is treatment-emergent. The event is considered treatment-emergent if both of the following 2 criteria are met:

- The AE onset is the same as or after the month and year (or year) of the first dosing date of study drug, and
- The AE onset date is the same as or before the month and year (or year) of the date corresponding to 30 days after the date of the last dose of study drug

An AE with completely missing onset and stop dates, or with the onset date missing and a stop date later than the first dosing date of study drug, will be considered to be treatment-emergent. In addition, an AE with the onset date missing and incomplete stop date with the same or later month and year (or year alone if month is not recorded) as the first dosing date of study drug will be considered treatment-emergent.

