7.1.6. Summaries of Adverse Events and Deaths

Treatment-emergent (TE) AEs will be summarized based on the Safety Analysis Set for the BD Phase, and the LT analysis. TEAEs in the OLE Phase will be summarized based on the OLE Analysis Set. In LT analysis, TEAEs will be those included in BD Phase/OLE Phase summary.

The number and percentage of subjects who experienced at least 1 TEAE will be provided and summarized by SOC, PT, and treatment group. For other AEs described below, summaries will be provided by SOC, PT, and treatment group:

- TEAEs of Grade 3 or higher
- TEAEs by severity
- All TE treatment-related AEs
- TE Treatment-related AEs of Grade 3 or higher
- TE Treatment-related AEs by severity
- All TE SAEs
- All TE treatment-related SAEs
- All TEAEs leading to premature discontinuation of study drug
- All TEAEs leading to death (ie, outcome of death)

- All TEAEs leading to dose interruption of study drug
- All TEAEs leading to dose reduction of study drug (OLE Phase only)
- All AEs recorded between screening and prior to first dose of study drug

A brief, high-level summary of TEAEs, TEAEs with Grade 3 or Higher, TEAEs Related to Study Drug, TEAEs Related to Study Drug with Grade 3 or Higher, TE Serious AEs, TE Serious AEs Related to Study Drug, and TEAEs Leading to Premature Discontinuation of Study Drug will be provided by treatment group and by the number and percentage of subjects who experienced the above AEs. All deaths observed in the study will be also included in this summary.

Multiple events will be counted only once per subject in each summary. Adverse events will be summarized and listed first in alphabetic order of SOC, and then by PT in descending order of frequency of BD GS-9674 100 mg group within each SOC in the BD Phase/ total frequency within each SOC for the OLE Phase/ frequency of LT GS-9674 initially in 100 mg group in the long-term summary. For summaries by severity grade, the most severe grade will be used for those AEs that occurred more than once in an individual subject during the study.

In addition to the above summary tables, the following tables will be summarized by PT only, in descending order of frequency in the GS-9674 100 mg group in the BD Phase/ total frequency for the OLE Phase/ frequency of LT GS-9674 initially in 100 mg group in the long-term summary:

- All TEAEs
- TEAEs of Grade 3 or higher
- TE treatment-related AEs
- TE treatment-related AEs of Grade 3 or higher
- All TE SAEs

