Treatment-emergent laboratory abnormalities are defined as values that increase at least 1 toxicity grade from baseline at any postbaseline time point, up to and including the date of last dose of study drug plus 30 days in the BD Phase (and on or before the first dose of the OLE Phase)/OLE Phase for subjects who permanently discontinued study drug, or the last available date in the database snapshot for subjects who were still on treatment at the time of an interim analysis. LT analysis will include data summarized in BD Phase/OLE Phase. Data obtained after the last dose of study drug plus 30 days in the BD (and prior to first dose date of OLE Phase)/OLE Phase will not be included in the evaluation of the TE laboratory abnormalities in the LT analysis. If the relevant baseline laboratory value is missing, any abnormality of at least Grade 1 observed within the time frame specified above will be considered treatment-emergent.

7.2.2.2. **Treatment-Emergent Marked Laboratory Abnormalities**

Treatment-emergent marked laboratory abnormalities are defined as values that increase from baseline by at least 3 toxicity grades at any postbaseline time point, up to and including the date of the last dose of study drug plus 30 days in BD Phase (and on or before the first dose of OLE Phase)/OLE Phase for subjects who permanently discontinued study drug or the last available date in the database snapshot for subjects who were still on treatment at the time of an interim analysis. LT analysis will include data summarized in BD Phase/OLE Phase. Data obtained after the last dose of study drug plus 30 days in the BD (and prior to first dose date of OLE Phase)/OLE Phase will not be included in the evaluation of the TE laboratory abnormalities in the LT analysis. If the relevant baseline laboratory value is missing, any Grade 3 or 4 values observed within the timeframe specified above will be considered treatment-emergent marked abnormalities.

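### The TEAE definition has no worsening clause, so an AE that starts before dosing and worsens on study drug is left out of the TEAE tables if it stays on its original record

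*SAP*

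**What the plan says.** Section 7.1.5.1 requires one or both of two conditions. The first concerns onset: "Any AEs with an onset date on or after the study drug start date". That window closes 30 days after treatment is permanently stopped. It is applied by phase and, for the BD Phase, cut off at the first OLE dose. The second condition is "Any AEs leading to premature discontinuation of study drug in the BD/OLE phase". Severity, seriousness and other actions taken with study drug do not enter the definition.

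Section 7.1.5.2, on incomplete dates, also works from onset: "The AE onset is the same as or after the month and year (or year) of the first dosing date of study drug" is one of its two conditions.

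Section 7.1.6 restricts its on-treatment AE tables to TEAEs: overall incidence, Grade 3 or higher, by severity, treatment-related, serious, leading to discontinuation, leading to death, leading to interruption and, for the OLE Phase, leading to dose reduction. The one AE table outside that restriction is "All AEs recorded between screening and prior to first dose of study drug".

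The laboratory rule in section 7.2.2.1 is built differently. It counts "values that increase at least 1 toxicity grade from baseline at any postbaseline time point".

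**The concern.** Section 1.1 gives safety and tolerability as the primary objective, and the TEAE tables are its main between-group display. Section 1.2 describes the BD Phase thus: "Includes a 4-week screening period, 12 weeks of blinded treatment". The procedures table in Appendix 1 collects AEs from screening onward, so AE records with an onset before the first dose are expected.

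If such an event is mild at first dose and becomes Grade 3 or serious on study drug, a safety table should show the change. Under the stated definition it does not, unless the event ends treatment. Even an event that the investigator marks as related would be missing from the treatment-related tables, because these too are limited to TEAEs.

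**Working it through.** The SAP gives no figure to reproduce. The check applies the definition to one case and then looks for any other rule that would bring the case in.

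**Case.** The AE has a complete onset date in screening and is Grade 1 at first dose. On study drug it reaches Grade 3 or becomes serious, or dosing is interrupted because of it. Study drug is not permanently discontinued. The event remains one record with its original onset date.

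| SAP rule | Does it capture the case? |
|---|---|
| 7.1.5.1, onset condition | No: onset is before the first dose |
| 7.1.5.1, discontinuation condition | No: treatment continues |
| 7.1.5.2, incomplete dates | No: the onset date is complete |
| 7.1.6, worst-grade rule | No: it selects a grade for repeated events within a summary and does not change treatment-emergent status |
| 7.2.2.1, laboratory rule | Only for graded laboratory values, not for AE records |

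The worst-grade rule reads "For summaries by severity grade, the most severe grade will be used for those AEs that occurred more than once in an individual subject", so it operates only on events already admitted to a table.

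**Where the event does appear.** It is in the pre-dose AE table. It is also in the section 7.1.6 listings of all AEs (with a treatment-emergent flag), AEs of Grade 3 or higher, SAEs and AEs leading to interruption, none of which is limited to TEAEs. If fatal, it is in the count of all deaths in the high-level summary.

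**Second phase.** Section 7.1.5.1 is applied by phase. An AE that began in the BD Phase and worsens on open-label GS-9674 has its onset before the first OLE dose, so it is not an OLE TEAE unless it leads to discontinuation. For subjects first on GS-9674, an event that was a BD TEAE still enters the long-term tables, because section 7.1.6 carries BD and OLE TEAEs into that analysis. For subjects first on placebo this does not help: long-term groups 9 and 10 in section 3.2 exclude them.

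**Scale.** Planned arm sizes in section 1.2 are 20, 20 and 10. The change in a table's percentage is the number of omitted subjects divided by the group size.

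| Omitted subjects in the group | GS-9674 arm (20) | Pooled GS-9674 (40) | Placebo (10) |
|---|---|---|---|
| 0 | 0 | 0 | 0 |
| 1 | 1/20 = 5 points | 1/40 = 2.5 points | 1/10 = 10 points |
| 2 | 2/20 = 10 points | 2/40 = 5 points | 2/10 = 20 points |

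The counts 0 to 2 are an assumption made to show scale, since the SAP gives no rate. The changes are upper limits for a given table. Section 7.1.6 counts a subject once per summary, so a subject with another qualifying TEAE leaves that row unchanged.

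**The case against.** The strongest objection is that the outcome depends on a recording convention outside the SAP. If the protocol or CRF instructions require a new AE record with a new onset date at each worsening, the first bullet captures it and nothing is lost. This stands as a limit on size. It does not remove the point, because the SAP neither states the convention nor refers to it, and its definition gives the wrong count without it.

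A second objection is that a worsening clause may not be computable. A record with one onset date and one worst grade does not show when the grade rose. This also stands, and the fix needs a rule for that situation.

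Third, much on-treatment worsening is tabulated elsewhere: laboratory grades in 7.2.2.1, liver criteria in 7.2.3, and rises of at least 2 points from nadir in the partial Mayo score in 7.6.1. This narrows the gap to other clinical AEs and to the AE tables themselves.

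Four stronger readings are tempting, and the SAP does not support them:

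- **The event is hidden from the report.** It is lost from the TEAE tables, but the listings keep it and can be read in full at about 50 subjects.
- **An on-drug grade would be shown as pre-dose.** The pre-dose AE table is specified by SOC, PT and treatment group only, with no grade.
- **The laboratory rule contradicts the AE rule.** Laboratory values are repeated measurements without an onset date, so a different rule is to be expected. The comparison shows that the SAP counts worsening where it can measure it, not that two sections conflict.
- **The between-arm comparison is biased in a known direction.** Each arm's count can only fall, but the same rule applies to all arms, so the direction of any effect on the difference is unknown.

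Nor does scoring itch and bowel symptoms at baseline show that such symptoms would be AEs with onset in screening. They may be medical history instead.

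**Conclusion.** The point holds on the SAP's text. No rule in it counts as treatment-emergent an AE with a known onset before the first dose of the phase that worsens on study drug, keeps its original record and does not end treatment. The loss is confined to the TEAE tables.

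The size is uncertain. It is zero under a new-record convention. Otherwise it is up to 5 points per subject in a 20-subject arm and 10 points in the placebo arm for a given table, with an unknown number of subjects. Because these tables serve the primary objective and the correction is small, the definition should be changed, but the finding does not show that any event will in fact be lost.

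**What to change.** Add a third bullet to 7.1.5.1. It should count as treatment-emergent any AE with onset before the first dose of the phase that, on or after that dose and within the same 30-day limit (for the BD Phase, also before the first OLE dose), does any of the following:

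- increases in severity grade;
- becomes serious;
- leads to study drug interruption or reduction.

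Name the data sources: a new AE record, a dated grade change, the date of seriousness, or the action taken with study drug. Where the date of worsening is not recorded, count the event as treatment-emergent if its recorded worst grade cannot be shown to pre-date dosing.

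Alternatively, if the protocol or CRF instructions already require a new AE record with its own onset date at each worsening, one sentence in 7.1.5.1 saying so is enough.

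The cost is one bullet or sentence and a small change to the AE derivation. With the default for undated worsening, no new data are needed. The downside is that some natural fluctuation of pre-existing events will be counted. Section 1 says the SAP is finalised before unblinding for the primary analysis, so the rule should be settled by then. A later change would have to be documented in the CSR.
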